## 6 STATISTICAL METHODOLOGY AND STATISTICAL ANALYSES

This analysis will compare effectiveness outcomes of real-world progression-free survival (rwPFS) as primary outcome and Overall survival (OS) tumor response and time to next line of anti-cancer therapy/chemotherapy as secondary outcomes (depending on the availabilities of the data) in female patients treated with Palbociclib + Letrozole as first line MBC therapy versus Letrozole alone.

Means, medians, and standard deviations will be provided for continuous variables. Counts and percentages will be provided for dichotomous and polychotomous variables. Appropriate tests (t-tests and chi-square tests) will be provided for baseline demographic and clinical characteristics.

Inverse probability treatment weighting (IPTW) will be used to balance baseline demographic and clinical characteristics and to adjust analyses for differences in observed potential confounders between the two study cohorts. The balance in important prognostic baseline characteristics will be assessed using a standardized differences approach, with values  $\geq 0.10$  indicating a non-negligible imbalance.

Propensity scores for use in IPTW will be calculated using a multivariable logistic regression model based on the following proposed baseline covariates such as age, race, practice type, type of MBC, ECOG performance score, disease stage at diagnosis (I–IV or unknown/undocumented), number of disease sites at MBC diagnosis (1, 2,  $\geq 3$ ), bone-only metastases, visceral metastases, and individual Charlson comorbidities, depending on data availability. Stabilized weights based on the propensity scores will be computed. The final list of variables to be used in the propensity score model will be discussed and determined during analysis development, after reviewing pre-matched descriptive tables. The selection of covariates for analysis will be based on the study team's clinical judgment.

The Kaplan-Meier method adjusted for weighted stabilized IPTW scores and 95% confidence intervals (CIs) will be used to estimate median rwPFS. Cox proportional hazards analyses adjusted for weighted stabilized IPTW scores will be used to estimate hazard ratios and 95% CIs for PFS.

The Kaplan-Meier method and 95% CIs will be used to estimate:

- proportions of patients surviving by cohort at follow-up years 1 through 4.

The Kaplan-Meier method adjusted for weighted stabilized IPTW scores and 95% CIs will be used to estimate:

- median duration of treatment.

Cox proportional models with a robust sandwich estimator will be used to compare the risk of PFS and OS between the matched study cohorts. The Cox model proportionality assumption will be evaluated by visually inspecting the Kaplan-Meier plot among the matched cohorts and confirmed by testing the significance of interactions between treatment modality and the log of time as well as each time-dependent covariate and the log of time. If the proportionality assumption is violated, an interaction term of time may be added.

PSM will be performed. A multivariable binomial logistic regression model will be used to generate the propensity scores. Individual patients in the Palbociclib + Letrozole vs Letrozole alone cohorts will be matched by closest propensity scores. The Nearest Neighbor method (without replacement and with a caliper of 0.01) will be used to select the matched samples.

All data analysis will be executed using statistical software SAS version 9.4.

## 6.1 SUMMARY OF ANALYSES

Outcome	Statistical Method	Covariates
Time to treatment discontinuation	Kaplan-Meier Plot , Cox regression, summary of reason for discontinuation. Descriptive analysis and multivariate analyses to examine factors associated with time to discontinuation if sample size is large enough . This outcome is not intended to be used as an effectiveness	Demographic and clinical characteristics
Time to next line of therapy	Kaplan-Meier Plot , Cox regression. Descriptive analysis and multivariate analyses to examine factors associated with time to next line of therapy if sample size is large enough . This outcome is not intended to be used as an effectiveness	Demographic and clinical characteristics

Time to chemotherapy	Kaplan-Meier Plot, Cox regression. Descriptive analysis and multivariate analyses to examine factors associated with time to chemotherapy if sample size is large enough. This outcome is not intended to be used as an effectiveness	Demographic and clinical characteristics
Initial dose of Palbociclib	Count of patients by initial dose level; summary of baseline and clinical characteristics by initial dose level; logistic regression of initial dose level on demographic and clinical characteristics; summary of rwTR by initial dose level; logistic regression of rwTR on initial dose level; KM estimates and Cox regression of rwPFS on initial dose level; KM estimates and Cox regression of time to treatment discontinuation on initial dose level; dose change from initial dose.	Demographic and clinical characteristics
Dose adjustment	Describe dose changes of Palbociclib from initiation to discontinuation. Sankey diagram will be used as appropriate. Factors associated with dose adjustment will be examined by univariate and multivariate analyses as appropriate. Clinical outcomes (i.e, rwPFS, OS, and tumor response) associated with dose adjustment will be explored by Kaplan-Meier Plot, Cox regression, or logistic regression as appropriate.	Demographic and clinical characteristics
rwPFS	Kaplan-Meier Plot, Cox proportional hazards model, IPTW/PSM	Demographic and clinical characteristics
OS	Kaplan-Meier Plot, Cox proportional hazards model, IPTW/PSM	Demographic and clinical characteristics
Tumor response	Descriptive analyses and logistic regression analyses, PSM/IPTW	Demographic and clinical characteristics

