9.7. Data Analysis

The primary and secondary objectives of the study are to describe patient characteristics, real-world treatment patterns and effectiveness of Palbociclib + AI as initial endocrine based therapy for metastatic breast cancer.

Descriptive analyses: For categorical variables (eg, region, race, and stage at initial diagnosis), data will include the frequency (number of cases) and percentage (%) of total patients observed in each category; for continuous variables (eg, age and time from initial breast cancer diagnosis to metastatic diagnosis), variables will be presented as the mean, standard deviation (SD), median, 25th and 75th percentiles and ranges (minimum and maximum) in some cases. The calculation of percentages will always include the missing category in the case of missing values. Continuous variables may be categorized into intervals, with the distribution of patients (N, %) provided.

Kaplan-Meier curves and landmark analyses will be performed to estimate real-world progression-free survival, overall survival, and time on treatment, time to next line of anti-cancer therapy, and time to first use of chemotherapy. Specifically, landmark time points are 3, 6, 12, 18, 24, 30, and 36 months for rwPFS and rwTR, 0.5, 1, 1.5, 2, 2.5, and 3 years for overall survival, and 3, 6, 12, 18, 24, 30, and 36 months for Time on Treatment with Palbociclib + AI and time to next ant-cancer therapy and to first use of chemotherapy. Ninety-five percent (95%) confidence intervals on the median rwPFS, overall survival, and treatment time will be reported.

The maximum real-world tumor response will be computed for each patient with at least one on-Palbociclib + AI treatment tumor assessment. If a patient has a maximum tumor response of a CR or PR, then the patient will be considered to be a responder. Response rate will be computed using the number of patients with a CR or PR as the numerator and the number of patients with at least 1 on-treatment tumor assessment as the denominator.

[figure not shown]
Subgroup analyses will be conducted according to age, ECOG performance (0, 1, ≥ 2), de novo metastatic, visceral, non-visceral, bone only, disease sites (1, 2, ≥ 3), menopausal status, prior endocrine therapy, prior chemotherapy, prior surgery, prior radiation therapy as appropriate based on availabilities of the data and sample sizes.

The following sensitivity analyses will be performed as appropriate:

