Time to treatment discontinuation	
 
The time from the start of a treatment to the time of treatment discontinuation for any reason in 1LOT
 
Start date: PAL/AI start date in 1LOT
 
End date: 
 
A. PAL/AI end date in 1LOT
 
B. 2LOT start date
 
C. Death date in 1LOT
 
D. Whichever came first
 
 
 
Censoring date: latest available drug administration or latest visit/activity date (lab, office, radiology, etc), end of study, or loss to follow-up, whichever came first.
 
2LOT start date 
 
A. Start date of adding any new anti-neoplastic (chemotherapy, target therapy (eg., Abemaciclib, Ribociclib), or endocrine therapy) if there is evidence of disease progression or after 60 days of index date if there is no evidence of disease progression.
 
B. AI discontinuation or exchange from one AI to another AI is not considered as 2LOT start if there is no evidence of disease progression
 
C. Exchange from one PAL to another CDK4/6i AI is not considered as 2LOT start if there is no evidence of disease progression.
 
D. 1LOT was not advanced if PAL and/or AI were paused or stopped and then restarted within 120. Different days (90, 120, and 180) will be used as sensitivity analyses.
 
 
 

Organ-level metastatic sites	Number of sites; Sites of metastases (bone, lung, liver, brain, distant lymph nodes, other) Visceral vs. non-visceral, bone only
Modified Charlson comorbidity index (CCI)	As defined in the Flatiron database
Effectiveness outcomes	
Overall survival (OS)	
Time in months from index date to death due to any cause or censoring date will be calculated.
 
Based on an improved understanding of the death information in Flatiron and a better understanding of the OS analysis in PALOMA-2 the following changes will be made to the OS outcome definition.
 
Event: Any death recorded by Flatiron in the data extract. Patients who did not die will be censored at the time of data cutoff.

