Real-world PFS (rwPFS)	
Time in months from index date to progression or censoring date will be calculated.
 
Based on improved understanding of the PFS analysis in PALOMA-2 the following changes will be made to the PFS outcome definition.
 
Event: Any death or disease progression (concluded by the treating clinician based on radiology, laboratory evidence, pathology, or clinical assessment). If patients did not die or have disease progression, they were censored at the date of initiation of next line of therapy for patients with two or more lines of therapy or their last visit date during the study period for patients with only one line of therapy.

Real-world tumor responses (rwTR)	
 
● Complete response: complete resolution of all visible disease.
 
● Partial response: partial reduction in size of visible disease in some or all areas without any areas of increase in visible disease.
 
● Stable disease: no change in overall size of visible disease; also included cases where some lesions increased in size and some lesions decreased in size
 
● Progressive disease: an increase in visible disease and/or presence of any new lesions; included cases where the clinician indicated progressive disease.
 

Response rate	
 
● Complete response or partial response divided by the number of patients with at least one tumor assessment while on the index treatment.
 

Time to next line of anti-cancer therapy	
 
● Defined as the time from the initiation of 1LOT (PAL+AI) until either 
 
○ the day before the start of 2LOT for patients with evidence of 2LOT, or
 
○ death if the death occurred within 60 days following the patient's last administration of 1LOT (PalB/AI)
 
○ Whichever occurred first.
 
 
 
● If a patient did not have evidence of 2LOT and did not die within the 60 days following the last 1LOT administration, the patient was censored at the latest available date that occurred on or before the end of study date of either last drug administration plus the number of days in a treatment cycle (last PAL/AI administration + 28 days) last visit date (e.g., office visit, lab, radiology, etc), or data cutoff date.
 

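### SAP 6.1 explores rwPFS, OS and response by dose adjustment without saying when a patient counts as adjusted; grouped as ever/never from index, rwPFS and OS carry immortal time bias

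*SAP*

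**What the plan says.** The Dose adjustment row of SAP 6.1 has a descriptive part, "Describe dose changes of Palbociclib from initiation to discontinuation", and an outcome part, in which rwPFS, OS and tumor response "associated with dose adjustment will be explored by Kaplan-Meier Plot, Cox regression, or logistic regression as appropriate". Its covariates are baseline characteristics.

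Both time-to-event outcomes in SAP 5.1 start at index. For OS: "Time in months from index date to death due to any cause or censoring date will be calculated". For rwPFS: "Time in months from index date to progression or censoring date will be calculated". Patients without an rwPFS event leave follow-up when a new line starts: "they were censored at the date of initiation of next line of therapy for patients with two or more lines of therapy".

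Protocol Table 1 defines a dose adjustment, counts days from index to the first one, and lists reductions and increases separately. It does not say how adjustment enters an outcome model.

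Three other places might seem to settle the timing, but do not:

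- Protocol 9.7: "Specifically, landmark time points are 3, 6, 12, 18, 24, 30, and 36 months for rwPFS and rwTR". These are times at which curves are read, not times at which patients are classified.
- SAP 6 mentions "each time-dependent covariate and the log of time", but as part of the proportional-hazards check for the matched treatment cohorts.
- The row directly above plans "KM estimates and Cox regression of rwPFS on initial dose level". Initial dose is known at index, so that analysis has no timing problem.

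**The concern.** If the methods of the initial-dose row are carried over to dose adjustment, patients are sorted at time zero by something that happens afterwards. A patient reaches the adjusted group only by staying progression-free, alive and on treatment until her dose changes. Anyone who progresses or dies sooner is counted as not adjusted. The adjusted group thus gains a stretch of follow-up with no possible event, and the other group collects the early failures. Adjusted patients look better even if adjustment does nothing.

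This is the only analysis of outcomes by dose adjustment in the visible plan, and its natural reading would be that patients whose dose was changed did as well or better. Because the distortion comes from the grouping, a purely descriptive Kaplan-Meier plot shows it too. SAP Section 1 says Amendment 3.0 was written after database lock, so an open grouping rule also leaves a choice that can be made with the data in hand.

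**Working it through.** **The plan's own figure.** None exists for dose adjustment. The only computed sample size is 138 per group for the cohort comparison (SAP 3.3). It is reproduced here only to check the event and follow-up model reused below.

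- Hazard ratio = 14.5/24.8 = 0.585.
- Freedman events = (1.960 + 1.282)² × [(1 + 0.585)/(1 − 0.585)]² = 153.
- Event probability per arm, with λ = ln 2/median: 1 − [exp(−3λ) − exp(−45.9λ)]/(42.9λ). The two arms average 0.548.
- 153/0.548/2 = 139.6 per group. The Lachin-Foulkes method gives 138.1. The model is consistent with the plan's.

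**Inputs from the documents.** Median rwPFS 24.8 months (SAP 3.3). Index dates 3 Feb 2015 to 31 Aug 2018 and cut-off 30 Nov 2018 give 3-45.9 months of potential follow-up; a later data release would lengthen this. There are 1,221 palbociclib + letrozole patients, 1,367 with any AI (Protocol 9.5). Alpha is two-sided 0.05 (SAP 3.2).

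**Assumed, because the documents give no values.** 25, 40 or 50% of patients prone to adjust; median time to change 1, 3 or 6 months, possible only before progression, discontinuation or censoring; 10% of rwPFS events are deaths; post-progression survival median 12 or 24 months; other discontinuation none or median 36 months. Adjustment has no effect.

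**By hand, middle case (40% prone, 3 months), without censoring or discontinuation.**

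- λ = ln 2/24.8 = 0.0279 and γ = ln 2/3 = 0.231 per month.
- Prone patients who change before failing: γ/(γ + λ) = 0.892. Adjusted share: 0.40 × 0.892 = 0.357.
- Their mean guaranteed event-free time: 1/(γ + λ) = 3.9 months.
- Adjusted: S₁(t) = [(γ + λ)exp(−λt) − λ exp(−(γ + λ)t)]/γ, which reaches 0.50 at 28.9 months.
- Not adjusted: S₀(t) = [exp(−λt) − 0.357 S₁(t)]/0.643, which reaches 0.50 at 22.3 months.

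Both true medians are 24.8. Simulation with censoring and discontinuation gives 28.5-28.8 and 22.6-23.0.

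**Simulation, 36 scenarios of 400,000 patients, true hazard ratio 1.** Between 16 and 48% of patients are actually adjusted.

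| Median time to change | Ever/never hazard ratio, rwPFS |
|---|---|
| 1 month | 0.86-0.91 |
| 3 months | 0.68-0.79 |
| 6 months | 0.58-0.69 |

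OS is within about 0.02 of these values (0.56-0.91 overall). The middle case gives 0.72-0.75 for rwPFS and 0.71-0.75 for OS. With 1,367 patients and 30% prone, rwPFS is 0.89, 0.75 and 0.65 at 1, 3 and 6 months.

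**Alternatives under the same null.**

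| Method | rwPFS | OS |
|---|---|---|
| On-treatment landmark, 3 or 6 months | 0.99-1.02 | 0.97-1.04 |
| Time-dependent covariate | 0.99-1.01 | 0.73-0.94 |

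- With 3,000,000 patients the landmark gives 0.99-1.00 for both outcomes.
- The time-dependent rwPFS figure assumes discontinuation is unrelated to progression risk. If it is related, the result is 0.95-1.00 when patients stay in rwPFS follow-up, and 0.99-1.01 when they are censored at discontinuation because the next line starts then.
- The time-dependent covariate fails for OS because patients who have progressed and stopped treatment remain at risk of death but can no longer be adjusted.
- For the same reason the landmark must be restricted to patients on treatment. With 40% prone and post-progression median 20 months, an unrestricted 6-month landmark gives OS 0.86-0.91; the restricted one gives 0.99-1.00.

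**False positives (illustration, 1,221 patients, two-sided 0.05).** Ever/never, rwPFS/OS: 18%/10% (25% prone, 1 month), 90%/52% (40%, 3 months), over 99%/91% (50%, 6 months). Landmark: 4-6%.

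**Response.** Assuming 45% potential responders, median 4 months to response and assessments every 3 months, the ever/never odds ratio is 1.00-1.20, against 0.98-1.02 with a landmark. Longer treatment gives more chances of both an adjustment and a recorded response.

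**Reductions and increases apart.** With 30% and 5% prone (medians 3 and 3-6 months), ever/never rwPFS hazard ratios are 0.76 and 0.68-0.76.

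**The case against.** The SAP never states ever/never groups or a fixed covariate. A time-dependent Cox model is Cox regression, and the row leaves the method to be chosen as appropriate. Protocol Table 1 already defines an adjustment, dates the first one and separates reductions from increases. The analysis is exploratory, Protocol 9.9 disclaims causal inference, SAP Section 1 names outcome associations only for initial dose, and SAP Section 7 lists no dose-adjustment output. The size rests on assumed frequency and timing. Parts of both documents are redacted. An on-treatment landmark needs a rule for treatment gaps.

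Much of this stands and limits the point. The defect is a missing specification whose plain reading is biased, not a stated error. The initial-dose row and the comparison with letrozole alone are untouched. The size cannot be fixed from the documents. Reasons for adjustment exist only for adjusted patients, so they can be reported but cannot serve as a covariate in an adjusted-versus-not model.

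It does not remove the point. The row shows no redaction, names a Kaplan-Meier plot first, and follows a row where grouping from index is correct. Table 1 supplies the date but not its use. The most obvious valid reading, a time-dependent covariate, still leaves OS biased. SAP 5.1 has a discontinuation definition from which on-treatment status can be built.

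**Conclusion.** The concern holds and the row should be changed. The visible plan does not say when adjustment status is assigned, and the ordinary use of the methods it names is biased for rwPFS and OS.

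Under the assumed ranges, the spurious hazard ratio runs from about 0.9 when changes cluster in the first month to below 0.6 when the median is 6 months and half the patients are prone. Timing matters most, and it is not documented. The immortal-time part always favours adjusted patients; confounding by the reason for adjustment could add to it or offset it, so the net direction in the real data is uncertain. The effect on response is small.

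**What to change.** In the Dose adjustment row of SAP 6.1:

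1. State when adjustment status is assigned, and exclude ever/never grouping from index.
2. For rwPFS and OS, name one on-treatment landmark in advance (for example 3 or 6 months). Include patients who are event-free and on treatment, classify them by adjustment up to then, and count outcomes afterwards in both the Kaplan-Meier curves and the Cox models. Define on-treatment from the SAP 5.1 discontinuation rule, and say how a patient in a treatment gap at the landmark is handled.
3. For rwPFS, a covariate that is 0 until the first change and 1 after it is an acceptable alternative, with an extended Kaplan-Meier plot if wanted. Note its slight bias if discontinuation tracks progression risk. Do not rely on it alone for OS.
4. Classify reductions and increases separately, as in protocol Table 1, and report recorded reasons. If increases are few, describe them only.
5. Report the response association as descriptive, or add the landmark as a sensitivity analysis.

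The cost is SAP wording and standard landmark or counting-process code; time to first change is already a planned variable. Under the assumptions, the landmark keeps 87-92% of patients at 3 months and 70-79% at 6, and ignores later changes. For response it keeps 71-75% and 50-56% once earlier responders are removed, or 57-64% and 40-48% if a later assessment is also required. With 1,221 patients, 30% prone to reduction and 5% to increase, about 158 reduced and 15-26 increased patients would be classified at 3 months, so results for increases would be imprecise.

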## 7 LIST OF TABLES AND FIGURES

Table 1. Summary of baseline demographic and clinical characteristic variables (unweighted and weighted results)

Figure 1. Kaplan Meier rwPFS curves

Table 2. Summary of rwPFS IPTW results

Figure 2. Kaplan Meier OS curves

Table 3. Summary of OS results

Figure 3. Kaplan Meier DOT curves

Table 4. Summary of DOT

